#### **Influenza and ARI incidence recording:**

Influenza and ARI incidence recording is performed during 6 months after immunization by means of follow-up and telephone calls to the study subjects.

A case of influenza and ARI is considered as a case of flu-like symptoms (according to: ECDC TECHNICAL DOCUMENT Protocol for case-control studies to measure pandemic and seasonal influenza vaccine effectiveness in the European Union and European Economic Area Member States / European center for Disease Prevention and Control, 2009):

*if a subject seeks physician's advice regarding unexpected occurrence of*

*- at least one of four systemic symptoms: 1) chills or fever, 2) distress, 3) headache, 4) myalgia and*

*- - of at least one of three respiratory symptoms: 1) cough, 2) sore throat, 3) respiratory distress.*

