***Systemic reactions:***

1. Increase of body temperature over 37 °C
2. Malaise
3. Headache
4. Sleep disturbance
5. Appetite disturbance
6. Nausea
7. Vomiting
8. Abdominal pains
9. Stuffy nose

---

Strictly confidential. Proprietary Information.  
[name]

10. Cough
11. Pharynx hyperaemic
12. Increased sweating
13. Tremor
14. Myalgia, arthralgia.

The nature and duration of immunization reactions in vaccinated subjects is compared upon interpretation of all study materials. An analysis of this data will make it possible to formulate a conclusion and resolve the issue of tolerability of study vaccines.

The course of the post-immunization period is assessed as smooth or complicated. Complicated course of the post-immunization period is considered as integration of intercurrent diseases after immunization. The absence of intercurrent diseases is considered as smooth post-immunization period. Fever responses were classified by temperature increase as follows: mild (low-grade fever up to 37.5 °C), moderate (temperature rise from 37.6 °C to 38.5 °C), and severe (temperature rise above 38.6 °C).

Local immunization reactions are classified as mild, moderate, and severe. Erythema without infiltration up to 50.0 mm in diameter at the injection site or infiltration up to 25.0 mm in diameter is estimated as a mild local reaction; erythema with a diameter more than 50.0 mm or an infiltrate with a diameter 26.0 to 50.0 mm was estimated as a moderate local reaction; infiltration more than 50.0 mm in diameter was estimated as a severe local reaction (Methodological Guidelines MU 3.3.2.1758-03 "Methods for determination of quality indicators of immunobiological products for prevention and diagnostics of influenza"). When the reaction is free of redness and/or infiltration, the reaction severity is accepted as indeterminate.

Local reactions will be assessed in all subjects, since local reactions were directly related to the administration of the vaccine.

Occurrence of general symptoms on the first 3 days after (and even on the day of immunization) may be associated with immunization (systemic reactions). However, it does not rule out their causal relationship with diseases, accidentally occurring within the first days of post-immunization period.

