According to the accepted methods of interpretation of the vaccinal process course, assessment of general reactions will only be performed in volunteers with a smooth course of vaccinal process, because in a complicated course of post-immunization process, the observed symptoms may be associated with an intercurrent disease rather than with immunization. Thus, in case of development of an infectious intercurrent disease, including ARD/ARI in a volunteer within the first days after immunization, the general symptoms observed should be excluded from systemic reactions recorded within the first 5 days.

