#### **7.3.1. Recording of adverse events**

Procedures for recording the AEs are described in Section 7.2. AEs are recorded in the source medical documentation of a study subject, as well as in the respective sections of the CRF. Adverse events are recorded from the moment of administration of the first dose of the study product till the Study end visit.

The following information should be specified during recording of AEs:

- Nature of AEs (preferably with indication of the diagnosis, rather than the list of symptoms).
- Time of AE onset (*day, month, year, hour, minute*, where possible).
- Time of AE resolution (*day, month, year, hour, minute*, where possible).
- Severity of AE (*mild, moderate, severe*).

---

Strictly confidential. Proprietary Information.  
[name]

- Association with the study drug administration (*doubtful, possible, probable, definite*);
- Incidence of AEs (*single, intermittent*);
- Measures taken with regard to AE (*none, change of the study drugs dosing regimen, suspension of the study drugs administration, withdrawal of the study drugs, concomitant therapy*);
- Compliance of AE with SAE criteria (see Section 7.3.2; *yes, no*).
- Outcome of AE (*resolved without residual complications; resolved with residual complications; observed during the Study end visit; death of a study subject; lost to follow-up; stabilization of AE and its consequences*).

The investigator should try to establish the diagnosis based on the signs, symptoms, and other clinical information. If a diagnosis is determined, then the diagnosis itself should be recorded as an AE. If the diagnosis is unknown, then each complaint and symptom must be recorded as a separate AE.

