#### *Safety analysis*

The safety analysis will be conducted by descriptive methods in the safety population. Adverse events will be coded using MedDRA. The number (percentage) of participants with AEs and the number of AEs will be presented in tables by system organ class and preferred term, as well as by the study therapy and severity.

---

Strictly confidential. Proprietary Information.  
[name]

With that, within a system organ class and preferred term, each subject will be considered once with regard to study therapy and maximum severity. The number (percentage) of volunteers with local and general reactions to vaccination will be presented taking into account severity and duration.

Laboratory findings and their changes after vaccination compared to the baseline and “shift tables” relative to normal values will be tabulated by therapeutic groups and by assessment points.

The results of the assessment of vital functions will be tabulated by therapeutic groups for each assessment point together with changes from the last available measurement prior to vaccination.

The results of physical examination will be presented descriptively by therapeutic groups and by assessment points.

Immunological parameters evaluation results: serum immunoglobulin content (ELISA: IgE) and their changes after vaccination compared to baseline values will be tabulated by therapeutic groups.

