### **8.5. Selection of study subjects**

Data analysis is performed in the following populations:

**Safety analysis population.** This population will include all volunteers who received a dose of the vaccine. The whole safety analysis will be provided in that population of volunteers.

**Full Analysis Set (FAS).** This analysis set will include all volunteers from the safety analysis set who had at least one measurement of serum antibody titer to antigens made. This analysis set was used for the analysis of efficacy and immunogenicity.

**Per-protocol population.** This population includes all the volunteers from the full analysis set meeting the inclusion / non-inclusion criteria, having received a dose of the vaccine according to the randomization, who provided data before and after vaccination to asses immunogenicity according to the study schedule, who did not receive any of the prohibited drugs, and who completed the study without any significant protocol deviations. This analysis set will be used for the analysis of immunogenicity parameters.

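### Section 7.2 assesses systemic reactions only in smooth-course volunteers, while sections 8.1 and 8.5 analyse everyone vaccinated, and the exclusion rule can be applied in more than one way

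*Combined protocol and SAP*

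**What the plan says.** **Section 7.2, reactogenicity.** Under the list of systemic reactions, local reactions are assessed in everyone: "Local reactions will be assessed in all subjects". Systemic reactions are treated differently: "assessment of general reactions will only be performed in volunteers with a smooth course of vaccinal process". A smooth course is defined without a time limit: "The absence of intercurrent diseases is considered as smooth post-immunization period". The next sentence of the rule takes an infectious intercurrent disease, including ARD/ARI, arising in the first days, and says that "the general symptoms observed should be excluded from systemic reactions recorded within the first 5 days". Reactions are assessed before vaccination, at 2 hours and daily for 5 days. The text also says that general symptoms in the first 3 days may be linked to vaccination.

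**Section 8.1, Safety analysis.** The analysis is descriptive and uses the safety population. "The number (percentage) of volunteers with local and general reactions to vaccination will be presented taking into account severity and duration". No restriction to smooth-course volunteers is given.

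**Section 8.5.** The safety population is everyone who received a dose. "The whole safety analysis will be provided in that population of volunteers". No smooth-course subset is defined.

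**Section 7.3.1.** For adverse events: "If a diagnosis is determined, then the diagnosis itself should be recorded as an AE". Symptoms are entered separately only when no diagnosis is known.

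**The concern.** The percentage with systemic reactions has two prescribed denominators. Three further features make the rule hard to apply in one way.

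- **Unit.** The first sentence of the rule removes volunteers. The second removes only symptoms.
- **Disease type.** The definition of a smooth course, and the first sentence, refer to any intercurrent disease. The second sentence refers to an infectious one.
- **Onset window.** It is only loosely given. In context it reads as about 3 to 5 days.

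Entry into the analysis also rests on a judgement made after vaccination, about symptoms that partly overlap the reactions being counted. Raised temperature and cough are both listed systemic reactions. Fever with cough also meets the symptom part of the influenza/ARI definition in section 6.2, which asks for a systemic symptom and "of at least one of three respiratory symptoms: 1) cough, 2) sore throat, 3) respiratory distress". That definition further requires contact with a physician, so fever, headache or myalgia alone does not meet it. Section 7.2 does not refer to the definition.

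Reactogenicity is a stated purpose, the study is registrational, and section 7.2 intends these data to settle tolerability. With no hypothesis test planned, the reported percentages are the result. The restriction could shift them in an unknown direction.

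**Working it through.** **1. Phase I figures (section 1.2, Clinical studies).** Phase I applied an explicit version of the rule: whole subjects removed, any intercurrent condition, five days. It kept 29 of 30 (Quadri), 28 of 30 (Plus) and 29 in the placebo group. The stated rates reproduce:

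- Quadri 6/29 = 20.7%
- Plus 1/28 = 3.6%
- placebo 3/29 = 10.3%

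Two-sided Fisher tests give p = 0.102 (Quadri against Plus) and p = 0.470 (Quadri against placebo), matching the text. The Quadri–Plus difference as analysed is 20.7 − 3.6 = 17.1 points.

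**2. Phase I on all 30 per group.** One Quadri and two Plus subjects return, each either a reactor or not. Quadri becomes 6 or 7 of 30, and Plus becomes 1, 2 or 3 of 30.

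| Quadri | Plus | Difference (points) | Fisher p |
|---|---|---|---|
| 6/30 | 1/30 | 16.7 | 0.103 |
| 6/30 | 2/30 | 13.3 | 0.254 |
| 6/30 | 3/30 | 10.0 | 0.472 |
| 7/30 | 1/30 | 20.0 | 0.052 |
| 7/30 | 2/30 | 16.7 | 0.146 |
| 7/30 | 3/30 | 13.3 | 0.299 |

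The difference lies between 10.0 and 20.0 points. Quadri is higher throughout, and no scenario falls below p = 0.05.

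**3. Two populations, two counts.** Raised temperature in the Quadri group was 3 of 30 in the adverse-event table (section 1.3, Table 1). In the smooth-course analysis it was 6.9% of 29 = 2. Onset after the five days is another possible explanation, so this does not prove an effect of the subset.

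**4. Scale in this trial (assumption: phase I's excluded fraction carries over).** Taking placebo as 29 of 30, the excluded fraction is e = 4/90 = 4.4%, with exact (Clopper–Pearson) 95% CI 1.2 to 11.0%. Then 612 × e is about 27 volunteers (7 to 67), and 204 × e is about 9 per arm.

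Let r be the rate among smooth-course volunteers.

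- Volunteers removed: r
- Symptoms only removed, all vaccinated in the denominator: r(1 − e)
- All symptoms counted in all vaccinated: from r(1 − e), if no excluded volunteer has a listed symptom, to r(1 − e) + e, if every one does
- Shift relative to r: −re to +(1 − r)e

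| r | e | Symptoms removed | All counted | Shift (points) |
|---|---|---|---|---|
| 20.7% | 4.4% | 19.8% | 19.8 to 24.2% | −0.9 to +3.5 |
| 3.6% | 4.4% | 3.4% | 3.4 to 7.9% | −0.2 to +4.3 |
| 20.7% | 11.0% | | | −2.3 to +8.7 |
| 3.6% | 11.0% | | | −0.4 to +10.6 |

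At e = 4.4% the unit question moves a rate by 20.7 − 19.8 = 0.9 points or 3.6 − 3.4 = 0.2 points. At e = 1.2% no shift exceeds 1.2 points.

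**The case against.** The best defence reads the second sentence of the rule as the working form of the first. Section 7.2 would then define what counts as a systemic reaction, and sections 8.1 and 8.5 would define who is analysed. This does not hold. The first sentence limits the assessment to certain volunteers in plain words, and the sponsor's own phase I study removed whole subjects.

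Other points carry more weight.

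- **Safeguards.** Blinding, daily examination to Day 5, adverse-event tables in all vaccinated volunteers, and intercurrent disorders as a separate safety parameter all reduce the problem. They do not remove it. An established diagnosis is entered in place of its symptoms, and no planned table shows the daily symptom data of volunteers with a complicated course. The symptom data are not lost, so the gap is in tabulation.
- **Comparison between arms.** Coincidental illness is balanced on average by randomisation, and the phase I direction survives every scenario. The upper shifts assume that every excluded volunteer is a reactor, and +10.6 also takes the upper confidence limit. These are bounds, not expectations.
- **Second table.** Showing reactions regardless of attribution goes beyond clarifying the wording, and section 7.2 gives a reason for leaving these symptoms out. The smooth-course analysis can stay. The added table makes visible what it removes.

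**Conclusion.** The concern holds, and the plan should be changed. Sections 7.2, 8.1 and 8.5 give conflicting populations for systemic reactions, and section 7.2 fixes neither the unit of exclusion nor the disease type. If phase I's excluded fraction of 4.4% applies and smooth-course rates resemble phase I's (3.6% or 20.7%), the denominator conflict moves an arm's rate by −0.9 to +4.3 points. At 11.0% excluded the range is −2.3 to +10.6. The unit ambiguity alone is under 1 point at 4.4%. The true excluded fraction in this trial is unknown, so these sizes are illustrative; the contradiction in the text does not depend on them. The effect is confined to descriptive reactogenicity counts and rates. The primary endpoint, sample size and alpha are unaffected.

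**What to change.** Reconcile section 7.2 with sections 8.1 and 8.5.

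1. Name in section 8 the denominator for general reactions.
2. Tabulate the listed systemic reactions through Day 5 in the safety population, regardless of attribution.
3. Present the smooth-course analysis beside it as a labelled subset defined in section 8.5. State whether volunteers or only symptoms are removed, which diseases count, and the onset window.
4. Classify volunteers before unblinding and report the number excluded per arm.

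The cost is wording in three sections and one extra table from data already collected in the daily assessments. The downside is small: some coincidental ARI symptoms will be counted, balanced across arms on average by randomisation.

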### **7.3. Reporting requirements, procedures for recording and reporting of adverse events and intercurrent diseases**

An **adverse event (AE)** is any adverse change of a study subject's condition upon administration of the medicinal product, irrespective of the causal relationship with its administration. AEs include all adverse and unintended changes (e.g., deviation of a laboratory parameter), symptoms or diseases, where the time of occurrence does not rule out the causal relationship with administration of the medicinal product (manifestations absent in a subject prior to enrollment and developing during participation in a study, or manifestations observed in a volunteer prior to enrollment, the severity of which increases during the study upon administration of study products), irrespective of relationship with administration of the medicinal product.

An **adverse drug reaction (ADR)**, with regard to pre-approval clinical use of a new medicinal product, includes all negative reactions associated with administration of any dose of the medicinal product. The term "associated with administration of the medicinal product" means at least a minimum possibility of presence of a causal relationship between the medicinal product and the adverse event, i.e. correlation cannot be excluded. For registered medicinal products, the term "adverse drug reactions" means all negative reactions associated with administration of the medicinal product in standard doses used for prevention, diagnostics, or treatment of diseases, as well as for modification of physiological functions.

#### **7.3.1. Recording of adverse events**

Procedures for recording the AEs are described in Section 7.2. AEs are recorded in the source medical documentation of a study subject, as well as in the respective sections of the CRF. Adverse events are recorded from the moment of administration of the first dose of the study product till the Study end visit.

The following information should be specified during recording of AEs:

- Nature of AEs (preferably with indication of the diagnosis, rather than the list of symptoms).
- Time of AE onset (*day, month, year, hour, minute*, where possible).
- Time of AE resolution (*day, month, year, hour, minute*, where possible).
- Severity of AE (*mild, moderate, severe*).

---

Strictly confidential. Proprietary Information.  
[name]

- Association with the study drug administration (*doubtful, possible, probable, definite*);
- Incidence of AEs (*single, intermittent*);
- Measures taken with regard to AE (*none, change of the study drugs dosing regimen, suspension of the study drugs administration, withdrawal of the study drugs, concomitant therapy*);
- Compliance of AE with SAE criteria (see Section 7.3.2; *yes, no*).
- Outcome of AE (*resolved without residual complications; resolved with residual complications; observed during the Study end visit; death of a study subject; lost to follow-up; stabilization of AE and its consequences*).

The investigator should try to establish the diagnosis based on the signs, symptoms, and other clinical information. If a diagnosis is determined, then the diagnosis itself should be recorded as an AE. If the diagnosis is unknown, then each complaint and symptom must be recorded as a separate AE.

#### **7.3.1.1. Evaluation of severity of adverse event**

The investigator should assess the severity of each AE using the following AE severity classification:

- mild: with or without symptoms, which are easily tolerated without treatment;
- moderate: minimum or local non-surgical treatment is indicated, may interfere with daily activities;
- severe: may interfere with daily activities, may require hospitalization or extension of existing hospitalization.

If severity of the AE changed in the course of its development, maximum severity should be reported.

#### **7.3.1.2. Evaluation of causal relationship between the adverse event and administration of the study product**

All available information which could help to reveal the causal relationship between the AE and the study product should be considered during evaluation of this relationship, namely:

- mechanism of action of the study product;
- information on known side effects according to the study protocol, investigator's brochure, and draft instruction for medical use of the product;
- characteristic of AE;
- temporal association of AE with the product administration;
- time of AE resolution;

Strictly confidential. Proprietary Information.  
[name]

- AE resolution upon withdrawal of the product or down titration;
- administration of other medicinal products or effect of chemical substances;
- natural course of the main disease or other conditions;
- study procedures;
- effect of other factors.

Based on analysis of the obtained information, the investigator will determine the causal relationship between the AE and the study product using one of the following categories:

- Doubtful: Clinical manifestations of AE occur in absence of a clear temporal association with the product administration. Other factors (medicinal products, diseases, chemical substances) which may cause their occurrence are observed.
- Possible: Clinical manifestations of AE have a temporal association with the product administration, but they can be attributed to concomitant diseases or administration of other medicinal products and to the effect of chemical substances. Information on a reaction to the product withdrawal is ambiguous.
- Probable: Clinical manifestations of AE have a temporal association with the product administration, can hardly be attributed to concomitant diseases or other factors and decrease after the product withdrawal. The response to re-challenge of the product is unknown.
- Definite: Clinical manifestations of AE occur during the product administration and cannot be attributed to existing diseases and the effect of other factors. Manifestations of ARs decrease after the product is discontinued and reoccur upon its re-initiation.

AEs with a doubtful causal relationship with the study product are considered as not associated with the study product administration. AEs with a possible, probable, or definite causal relationship with the study product are considered as associated with the study product administration.

### 7.3.2. Serious adverse events

A SAE is any AE corresponding to one or several criteria listed below:

- AE causing death of a volunteer.
- AE posing a threat to life of a volunteer.
- AE requiring hospitalization of a study subject or leading to extension of existing hospitalization, except for:
  - Optional treatment.
  - Monitoring of the study disease.

---

Strictly confidential. Proprietary Information.  
[name]

- For procedures as per the protocol, not associated with a deterioration in a volunteer's condition.
- Treatment of the existing disease, associated or not associated with the study disease, which has not worsened after administration of the first dose of the study product.
- Treatment received in an emergency unit due to an event which does not comply with the above mentioned criteria and which did not lead to hospitalization.
- AE leading to permanent or pronounced incapacity for work or disability.
- AE leading to congenital abnormalities / developmental diseases in children whose parents were exposed to the study product.

Apart from that, SAEs may include important medical manifestations in case when, based on the investigator's medical experience, such manifestations, if left untreated, may lead to one of the outcomes described above.

Death of a study subject is considered as an outcome of the AE. In case of death of a study subject, the investigator has to report medical condition of the study subject or the event causing the death, e.g., a disease, an accident, etc. as an SAE.

AE is considered as "posing a threat to life of a study subject" if it constitutes immediate danger to life of a study subject at the time of its development. This category does not include AEs, which could theoretically lead to subject's death if their severity was higher.

According to SAE criteria, hospitalization is considered as inpatient treatment for more than one calendar day, i.e. a hospital stay for at least one night.

